2. ABBREVIATIONS

Abbreviations pertain to the Statistical Analysis Plan (SAP) only (not the tables, figures and listings [TFLs]).

ABP	Ambulatory blood pressure
ABPM	Ambulatory blood pressure monitoring
AE	Adverse event
ALP	Alkaline phosphatase
ALT	Alanine aminotransferase
AUC	Area under the concentration versus time curve
AUC(0-∞)	Area under the concentration versus time
AUC(0-t _{last})	Area under the concentration versus time curve from time zero to time t, where t is the last time point with a measurable concentration
%AUC(t _{last} -∞)	Percentage of AUC(0-∞) extrapolated
BQL	Below lower limit of quantitation
CI	Confidence interval
C _{max}	Maximum observed drug concentration
CL/F	Apparent total body clearance of drug calculated after extra-vascular administration
CRF	Case Report Form
CSR	Clinical Study Report
CRU	Clinical Research Unit
CV	Coefficient of variation
DBP	Diastolic blood pressure
EC	Early Clinical
ECG	Electrocardiogram
e.g.	For example (Latin: exempli gratia)
ICH	International Council on Harmonisation
LLOQ	Lower limit of quantification
LS	Least square
MAP	Mean arterial pressure
MedDRA	Medical Dictionary for Regulatory Activities

MRE	Magnetic resonance elastography
PK	Pharmacokinetic
PR	Pulse rate
SAP	Statistical Analysis Plan
SBP	Systolic blood pressure
SD	Standard deviation
SOP	Standard Operating Procedure
TBL	Total bilirubin
TFLs	Tables, Figures, and Listings
$t_{1/2}$	Half-life associated with the terminal rate constant (λ_z) in non-compartmental analysis
t_{max}	Time of maximum observed drug concentration
ULN	Upper limit of normal
V_{ss}/F	Apparent volume of distribution at steady state after extra-vascular administration
V_z/F	Apparent volume of distribution during the terminal phase after extra-vascular administration
WHO	World Health Organization

3. INTRODUCTION

This SAP has been developed after review of the Clinical Study Protocol (final version dated 17 August 2017) and Protocol Amendment (c) (final version dated 20 October 2017).

This SAP describes the planned analysis of the safety, tolerability and pharmacokinetic (PK) data from this study. A detailed description of the planned TFLs to be presented in the clinical study report (CSR) is provided in the accompanying TFL shell document.

The intent of this document is to provide guidance for the statistical and PK analyses of data. In general, the analyses are based on information from the protocol, unless they have been modified by agreement between Eli Lilly and Company and Covance Early Clinical (EC) Biometrics. A limited amount of information concerning this study (e.g., objectives, study design) is given to help the reader's interpretation. This SAP must be signed off prior to first subject administration for this study. When the SAP and TFL shells are agreed upon and finalized, they will serve as the template for this study's CSR.

This SAP supersedes the statistical considerations identified in the protocol; where considerations are substantially different, they will be so identified. If additional analyses are required to supplement the planned analyses described in this SAP, they may be performed and will be identified in the CSR. Any substantial deviations from this SAP will be agreed upon between Eli Lilly and Company and Covance EC Biometrics and identified in the CSR. Any minor deviations from the TFLs may not be documented in the CSR.

This SAP is written with consideration of the recommendations outlined in the International Council on Harmonisation (ICH) E9 Guideline entitled Guidance for Industry: Statistical Principles for Clinical Trials¹ and the ICH E3 Guideline entitled Guidance for Industry: Structure and Content of Clinical Study Reports².

4. STUDY OBJECTIVES

4.1 Primary Objective

- To compare and contrast the cardiovascular effects of lasmiditan 200 mg and sumatriptan 100 mg administered together to the cardiovascular effects of single doses of either drug administered alone.

4.2 Secondary Objectives

- To evaluate the PK of lasmiditan 200 mg and sumatriptan 100 mg administered either alone or together.
- To evaluate the safety and tolerability of lasmiditan 200 mg and sumatriptan 100 mg.

4.3 Exploratory Objective

- To evaluate the effect of lasmiditan on renal function biomarkers in serum and urine.
- To evaluate the PK of lasmiditan metabolites alone and in combination with sumatriptan in healthy subjects.

5. STUDY DESIGN

This is a randomized, double-blind, crossover study with 4 study periods in healthy subjects. All subjects will participate in 4 treatment periods. The treatments are as follows:

- Treatment A: lasmiditan 200 mg + sumatriptan 100 mg
- Treatment B: lasmiditan 200 mg + placebo
- Treatment C: sumatriptan 100 mg + placebo
- Treatment D: placebo + placebo

Each subject will be randomized to one of 4 treatment sequences in a William's square design as outlined in Table 1.

Table 1. Sequences in Study LAHU

Sequence	Period 1	Period 2	Period 3	Period 4
1	Lasmiditan + sumatriptan	Lasmiditan + placebo	Sumatriptan + placebo	Placebo + placebo
2	Lasmiditan + placebo	Sumatriptan + placebo	Placebo + placebo	Lasmiditan + sumatriptan
3	Sumatriptan + placebo	Placebo + placebo	Lasmiditan + sumatriptan	Lasmiditan + placebo
4	Placebo + placebo	Lasmiditan + sumatriptan	Lasmiditan + placebo	Sumatriptan + placebo

Screening Period:

All subjects will participate in a screening visit up to 28 days prior to Period 1 study drug dosing.

Treatment Periods:

All subjects will participate in 4 treatment periods. Subjects will be randomized to one of 4 treatment sequences. They will be admitted to the clinical research unit (CRU) the day prior to dosing (Day -1) in Period 1, and will be dosed on Day 1 of each treatment period according to their assigned treatment sequence (Table 1). Subjects will be discharged from the CRU on Day 3 of Period 4 following the collection of all ambulatory blood pressure (ABP) measurements and PK blood samples.

There will be a washout of at least 4 days between each dosing day.

All subjects will be discharged from the study at least 5 days after discharge from Period 4.

6. TREATMENTS

The following is a list of the study treatment abbreviations that will be used in the TFLs.

Study Treatment Name	Treatment order in TFL
Placebo	1
200 mg lasmiditan + 100 mg sumatriptan	2
200 mg lasmiditan + placebo	3
100 mg sumatriptan + placebo	4

7. SAMPLE SIZE JUSTIFICATION

Up to 40 subjects may be enrolled to ensure 30 subjects complete the study. Assuming standard deviation for the change, within-subject, in systolic blood pressure (SBP) of 12.7 mmHg (based on results from study CCI [REDACTED]), this will result in a 90% probability that the half-width of the 90% confidence interval (CI) about the mean within-subject change between periods is no larger than 4.6 mmHg.

8. DEFINITION OF ANALYSIS POPULATIONS

The “Safety” population will consist of all enrolled subjects, whether or not they completed all protocol requirements.

The “Pharmacokinetic” population will consist of all subjects who received at least one dose of lasmiditan or sumatriptan and have evaluable PK data. Subjects may be excluded from the PK summary statistics and statistical analysis if a subject has an adverse event (AE) of vomiting that occurs at or before 2 times median time of maximum observed drug concentration (t_{max}).

All protocol deviations that occur during the study will be considered for their severity/impact and will be taken into consideration when subjects are assigned to analysis populations.

9. STATISTICAL METHODOLOGY

9.1 General

Data listings will be provided for all data that is databased. Summary statistics and statistical analysis will only be presented for data where detailed in this SAP. For continuous data, summary statistics will include the arithmetic mean, arithmetic standard deviation (SD), median, min, max and N; for log-normal data (e.g. the PK parameters: area under the concentration versus time curve [AUCs] and maximum observed drug concentration [C_{max}]) the geometric mean and geometric coefficient of variation (CV%) will also be presented. For categorical data, frequency count and percentages will be presented. Data listings will be provided for all subjects up to the point of withdrawal, with any subjects excluded from the relevant population

highlighted. Summary statistics and statistical analyses will generally only be performed for subjects included in the relevant analysis population. For the calculation of summary statistics and statistical analysis, unrounded data will be used.

Mean change from baseline is the mean of all individual subjects' change from baseline values. Each individual change from baseline will be calculated by subtracting the individual subject's baseline value from the value at the timepoint. The individual subject's change from baseline values will be used to calculate the mean change from baseline using a SAS procedure such as Proc Univariate.

Data analysis will be performed using SAS[®] Version 9.3 or greater.

9.2 Demographics and Subject Disposition

Subject disposition will be listed. The demographic variables age, sex, race, ethnicity, country of enrolment, site ID, body weight, height and body mass index will be summarized and listed.

9.3 Pharmacokinetic Assessment

9.3.1 Pharmacokinetic Analysis

PK parameter estimates will be determined using non-compartmental procedures in validated software program (Phoenix WinNonlin Version 6.4 or later).

Plasma concentrations of lasmiditan (LY573144), its metabolites, and sumatriptan will be used to determine the following PK parameters, when possible:

Parameter	Units	Definition
C_{\max}	ng/mL	maximum observed drug concentration
t_{\max}	h	time of maximum observed drug concentration
AUC(0- ∞)	ng.h/mL	area under the concentration versus time curve from time zero to infinity
AUC(0- t_{last})	ng.h/mL	area under the concentration versus time curve from time zero to time t , where t is the last time point with a measurable concentration
%AUC(t_{last} - ∞)	%	percentage of AUC(0- ∞) extrapolated
$t_{1/2}$	h	half-life associated with the terminal rate constant (λ_z) in non-compartmental analysis
CL/F	L/h	apparent total body clearance of drug calculated after extra-vascular administration (LY573144 and sumatriptan only)
V_z/F	L	apparent volume of distribution during the terminal phase after extra-vascular administration (LY573144 and sumatriptan only)
V_{ss}/F	L	apparent volume of distribution at steady state after extra-vascular administration (LY573144 and sumatriptan only)
MR		Metabolic ratio ^a

^a = no molar correction will be applied since the metabolites are very similar in molecular weight and within 5% of the molecular weight for lasmiditan.

Additional PK parameters may be calculated, as appropriate. The software and version used for the final analyses will be specified in the CSR. Any exceptions or special handling of data will be clearly documented within the final study report.

Formatting of tables, figures and abbreviations will follow the Eli Lilly Global PK/PD/TS Tool: NON-COMPARTMENTAL PHARMACOKINETIC STYLE GUIDE. The version of the tool effective at the time of PK analysis will be followed.

General PK Parameter Rules

- Actual sampling times will be used in the final analyses of individual PK parameters, except for non-bolus pre-dose sampling times which will be set to zero.
- C_{\max} and t_{\max} will be reported from observed values. If C_{\max} occurs at more than one time point, t_{\max} will be assigned to the first occurrence of C_{\max} .
- AUC parameters will be calculated using a combination of the linear and logarithmic trapezoidal methods (linear-log trapezoidal rule). The linear trapezoidal method will be applied up to t_{\max} and then the logarithmic trapezoidal method will be used after t_{\max} . The minimum requirement for the calculation of AUC will be the inclusion of at least three consecutive plasma concentrations above the lower limit of quantification (LLOQ), with at least one of these concentrations following C_{\max} . AUC(0- ∞) values where the

percentage of the total area extrapolated is more than 20% will be flagged. Any AUC(0-∞) value excluded from summary statistics will be noted in the footnote of the summary table.

- Half-life ($t_{1/2}$) will be calculated, when appropriate, based on the apparent terminal log-linear portion of the concentration-time curve. The start of the terminal elimination phase for each subject will be defined by visual inspection and generally will be the first point at which there is no systematic deviation from the log-linear decline in plasma concentrations. Half-life will only be calculated when a reliable estimate for this parameter can be obtained comprising of at least 3 data points. If $t_{1/2}$ is estimated over a time window of less than 2 half-lives, the values will be flagged in the data listings. Any $t_{1/2}$ value excluded from summary statistics will be documented in the footnote of the summary table.
- A uniform weighting scheme will be used in the regression analysis of the terminal log-linear portion of the concentration-time curve.
- The parameters based on predicted C_{last} will be reported.

Individual PK Parameter Rules

- Only quantifiable concentrations will be used to calculate PK parameters with the exception of special handling of certain concentrations reported below the lower limit of quantitation (BQL). Plasma concentrations reported as BQL will be set to a value of zero when all of the following conditions are met:
 - The compound is non-endogenous.
 - The samples are from the initial dose period for a subject or from a subsequent dose period following a suitable wash-out period.
 - The time points occur before the first quantifiable concentration.
- All other BQL concentrations that do not meet the above criteria will be set to missing.
- Also, where two or more consecutive concentrations are BQL towards the end of a profile, the profile will be deemed to have terminated and therefore any further quantifiable concentrations will be set to missing for the calculation of the PK parameters unless it is considered to be a true characteristic of the profile of the drug.

Individual Concentration vs. Time Profiles

- Individual concentrations will be plotted utilizing actual sampling times.
- The terminal point selections will be indicated on a semi-logarithmic plot.

Average Concentration vs. Time Profiles

- The average concentration profiles will be graphed using scheduled (nominal) sampling times.
- The average concentration profiles will be graphed using arithmetic average concentrations.
- The pre-dose average concentration for single-dose data from non-endogenous compounds will be set to zero.
- Concentrations at a sampling time exceeding the sampling time window specified in the protocol, or $\pm 10\%$, will be excluded from the average concentration profiles.
- Concentrations excluded from the mean calculation will be documented in the final study report.
- A concentration average will be plotted for a given sampling time only if 2/3 of the individual data at the time point have quantifiable measurements that are within the sampling time window specified in the protocol or $\pm 10\%$. An average concentration estimated with less than 2/3 but more than 3 data points may be displayed on the mean concentration plot if determined to be appropriate and will be documented within the final study report.

Treatment of Outliers during Pharmacokinetic Analysis

Application of this procedure to all PK analyses is not a requirement. Rather, this procedure provides justification for exclusion of data when scientifically appropriate. This procedure describes the methodology for identifying an individual value as an outlier for potential exclusion, but does not require that the value be excluded from analysis. The following methodology will not be used to exclude complete profiles from analysis.

Data within an Individual Profile

A value within an individual profile may be excluded from analysis if any of the following criteria are met:

- For PK profiles during single dosing of non-endogenous compounds, the concentration in a pre-dose sample is quantifiable.
- For any questionable datum that does not satisfy the above criteria, the profile will be evaluated and results reported with and without the suspected datum.

Data between Individual Profiles

1. If $n < 6$, then the dataset is too small to conduct a reliable range test. Data will be analyzed with and without the atypical value, and both sets of results will be reported.

2. If $n \geq 6$, then an objective outlier test will be used to compare the atypical value to other values included in that calculation:
 - a. Transform all values in the calculation to the logarithmic domain.
 - b. Find the most extreme value from the arithmetic mean of the log transformed values and exclude that value from the dataset.
 - c. Calculate the lower and upper bounds of the range defined by the arithmetic mean $\pm 3 \cdot SD$ of the remaining log-transformed values.
 - d. If the extreme value is within the range of arithmetic mean $\pm 3 \cdot SD$, then it is not an outlier and will be retained in the dataset.
 - e. If the extreme value is outside the range of arithmetic mean $\pm 3 \cdot SD$, then it is an outlier and will be excluded from analysis.

If the remaining dataset contains another atypical datum suspected to be an outlier and $n \geq 6$ following the exclusion, then repeat step 2 above. This evaluation may be repeated as many times as necessary, excluding only one suspected outlier in each iteration, until all data remaining in the dataset fall within the range of arithmetic mean $\pm 3 \cdot SD$ of the log-transformed values.

Reporting of Excluded Values

Individual values excluded as outliers will be documented in the final report. Approval of the final report will connote approval of the exclusion.

9.3.2 Pharmacokinetic Statistical Methodology

PK parameter estimates will be evaluated to determine the impact of a single oral dose of sumatriptan 100 mg on the PK of lasmiditan and its metabolites. Log-transformed C_{max} , $AUC(0-\infty)$, and $AUC(0-t_{last})$ will be evaluated using a linear effects model with fixed effects for treatment, period (1, 2, 3, or 4) and treatment sequence, and a random effect for subject. From this model, the 90% CI of the ratio of geometric means from Treatment A (lasmiditan + sumatriptan) will be determined and presented versus those of Treatment B (lasmiditan + placebo).

An example of the SAS code that will be used is as follows:

```
proc mixed data=xxx;
  by analyte;
  class trtmnt period seq subject;
  model l_pk = trtmnt period seq / alpha=0.1;
  random subject;
  lsmeans trtmnt / pdiff;
run;
```

where l_pk is the log-transformed (base e) PK parameter.

The t_{\max} will be analyzed using a Wilcoxon signed rank test. Estimates of the median difference based on the observed medians, 90% CIs, and the p-values from the Wilcoxon test will be calculated.

The same model will be independently used to assess the impact of a single oral dose of lasmiditan 200 mg on the PK of single oral dose of sumatriptan 100 mg.

Additional analyses may be performed, as warranted.

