10.1. Sample Size Determination

Up to 40 subjects may be enrolled to ensure 30 subjects complete the study. Assuming standard deviation for the change, within-subject, in SBP of 12.7 mmHg (based on results from study), this will result in a 90% probability that the half-width of the 90% confidence interval (CI) about the mean within-subject change between periods is no larger than 4.6 mmHg.

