10.3.2. Pharmacokinetic Analyses

10.3.2.1. Pharmacokinetic Parameter Estimation

Pharmacokinetic parameter estimates for lasmiditan, its metabolites, and sumatriptan will be calculated by standard noncompartmental methods of analysis and summarized using descriptive statistics.

The primary parameters for analysis will be C_{max} , t_{max} , AUC(0-tlast), and $AUC(0\text{-}\infty)$ of lasmiditan, its metabolites, and sumatriptan. Other noncompartmental parameters, such as half-life, apparent clearance, and apparent volume of distribution may be reported.

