10.3.2.2. Pharmacokinetic Statistical Inference

Pharmacokinetic parameter estimates will be evaluated to the impact of a single dose of sumatriptan 100 mg on the PK of lasmiditan and its metabolites. Log-transformed C_{max} and AUC parameters will be evaluated using a linear effects model with fixed effects for treatment, period (1, 2, 3, or 4) and treatment sequence, and a random effect for subject. From this model, the 90% CIs of the ratios of geometric means from Treatment A (lasmiditan + sumatriptan) will be determined and presented versus those of Treatment B (lasmiditan + placebo).

The t_{max} will be analyzed using a Wilcoxon signed rank test. Estimates of the median difference based on the observed medians, 90% CIs, and the p-value from the Wilcoxon test will be calculated.

The same model will be independently used to assess the impact of a single dose of lasmiditan 200 mg on the PK of sumatriptan.

Additional analyses may be performed, as warranted.

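### The t_max estimate is not tied to the signed-rank test: on its natural reading it is a difference of treatment medians, and no method is named for its 90% interval

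*SAP*

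**What the plan says.** SAP 9.3.2 states that t_max "will be analyzed using a Wilcoxon signed rank test", and continues: "Estimates of the median difference based on the observed medians, 90% CIs, and the p-values from the Wilcoxon test will be calculated". Protocol 10.3.2.2 has the same rule: "Estimates of the median difference based on the observed medians, 90% CIs, and the p-value from the Wilcoxon test will be calculated". The SAP therefore does not refine the protocol here.

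SAP 9.3.2 gives SAS code for the log-transformed C_max and AUC parameters but none for t_max. Neither document names a construction for the t_max interval. SAP section 11 reports no changes from the protocol's analyses.

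Protocol 10.3.2.1 lists t_max among the primary PK parameters. In the objectives table, PK sits under a secondary objective for the parent drugs and an exploratory one for the lasmiditan metabolites. SAP 9.3.1 derives individual PK parameters from actual sampling times.

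**The concern.** The signed-rank test works on within-subject differences. The estimate that belongs to it is the Hodges-Lehmann estimate, which is the median of all pairwise (Walsh) averages of those differences. The interval that belongs to it comes from inverting the same test.

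A difference of two treatment medians uses neither the pairing nor the ranks of the differences. It is a different quantity, in a crossover whose purpose is within-subject comparison. Estimate, interval and p-value could then appear on one line of a table while answering different questions. In some data sets the reported shift would lie outside the interval printed beside it.

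The wording also leaves two choices to the analyst: which median difference is meant, and how the interval is formed. A prespecified analysis should settle both before the data are seen.

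**Working it through.** **Inputs from the documents**
- Pairs: 30. SAP section 7: "Up to 40 subjects may be enrolled to ensure 30 subjects complete the study".
- Sampling grid (protocol Schedule of Activities): 0.5, 1, 1.5, 2, 2.5, 3, 4, 6, 8, 12 h.
- Sampling windows (note to that schedule): ±5 min up to 2 h, ±10 min from 2.5 to 6 h, ±20 min from 7 to 12 h.
- Lasmiditan t_max: about 1 to 2.5 h (protocol 3.2).

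**Inputs assumed**

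The documents give no t_max distribution and no within-subject correlation. I took t_max as lognormal with median 1.5–2 h, log-SD 0.45–0.6, true ratio between treatments 1–1.5, and correlation 0 or 0.5.

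**The plan's own figure**

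No design figure is stated for t_max. The only one in the documents concerns systolic pressure. Protocol 10.1 takes a within-subject SD of 12.7 mmHg and gives 90% assurance that the 90% interval's half-width will not exceed 4.6 mmHg. With n = 30:

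P(half-width ≤ 4.6) = P(χ²₂₉ ≤ 29 × [4.6 × √30 / (1.699 × 12.7)]²) = P(χ²₂₉ ≤ 39.53) = 0.908

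The stated 90% reproduces, and the t_max point does not touch it.

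**Quantities compared for t_max**
1. Difference of medians: median(A) − median(B).
2. Median of the paired differences: median(A − B).
3. Hodges-Lehmann: the median of the Walsh averages (dᵢ + dⱼ)/2 with i ≤ j. There are 30 × 31/2 = 465 of them.
4. Signed-rank 90% interval: the 152nd to the 314th ordered Walsh average (465 + 1 − 152 = 314).

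Hodges-Lehmann is the 233rd ordered value, so it lies inside (4) by construction. Quantity (1) has no such guarantee.

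**One illustrative data set**

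This is a simulated set of 30 pairs on the protocol grid, chosen to show the effect.

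| Quantity | Value |
|---|---|
| Treatment medians | 1.0 h and 2.0 h |
| Difference of medians | −1.0 h |
| Median paired difference | 0.0 h |
| Hodges-Lehmann | −0.25 h |
| Signed-rank 90% interval | −0.5 to 0.0 h |
| Wilcoxon p | 0.14 |

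The table would report a one-hour shift beside an interval that excludes it.

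**How often this happens**

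These results use 30 pairs and the lognormal assumptions above, with actual times spread within the protocol windows.

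| Result | Correlation 0 | Correlation 0.5 |
|---|---|---|
| Difference of medians outside the signed-rank 90% interval | about 1–5% | about 6–17% |

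Over all these settings:
- The mean absolute gap between the difference of medians and Hodges-Lehmann was about 0.1–0.26 h, or 6 to 16 minutes (0.26 × 60 = 15.6).
- The gap was at least 15 minutes in about 7–43% of trials.
- The median of the paired differences was outside the interval in at most 0.3%.
- Hodges-Lehmann was never outside.

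On nominal times the outside rate was about 0.5–12%, so using actual times does not remove the problem. As a sensitivity case I used a two-peak shape (peaks at 1 h and 2.5 h). It gave about 10–21% on nominal times and 16–29% on actual times.

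**The case against.** **The phrase may mean the median of the within-subject differences.** The text allows this. On that reading the pairing is respected and the estimate almost never leaves the signed-rank interval. The plural medians favour the treatment-median reading but do not settle it. What stands either way is that the estimator is not fixed, and neither reading gives the estimate that belongs to the test.

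**No interval method is named, so the interval might be built for the difference of medians itself.** A bootstrap interval, for example, would normally contain the estimate. It would then not correspond to the Wilcoxon p-value. The mismatch would move from between estimate and interval to between interval and test.

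**The 15-minute gap can be made to look large.** A reader who works on nominal times might infer that the two estimates differ by at least 15 minutes in about 60% of trials. Every grid time is a multiple of 0.5 h, so with 30 pairs both estimates are multiples of 0.25 h, and any disagreement at all is at least 15 minutes. SAP 9.3.1 uses actual times, for which the figure is about 7–43%.

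**The point is minor.** This stands. The documents give t_max no equivalence margin or decision rule. They do not say that it will decide whether coadministration delays absorption. Treatment medians are already planned as summaries in SAP 9.1.

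**Conclusion.** The point holds as under-specification with a probable mismatch. The test is paired and the interval method is unstated. The estimate, as most naturally read, is not the location the test addresses.

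A reader might infer that the reported estimate is bound to contradict its own interval. The documents do not support that. It requires both the treatment-median reading and an inverted signed-rank interval. Even then, under the lognormal assumptions and with actual times, it occurs in roughly 1–5% of trials at correlation 0 and 6–17% at 0.5. The percentages rest on assumed t_max distributions and depend strongly on the within-subject correlation, which the documents do not give. That the estimate can fall outside does not rest on them.

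A reader might also take the label of primary PK parameter to mean that a primary result is at risk. It is not: the blood-pressure and pulse-rate analyses and the sample size are unaffected. This is a desirable correction of low priority.

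**What to change.** In SAP 9.3.2, state that the t_max estimate is the Hodges-Lehmann estimate of the within-subject difference: A − B for lasmiditan and its metabolites, A − C for sumatriptan. Give it with the 90% interval obtained by inverting the same signed-rank test and with that test's p-value. Present the observed treatment medians as descriptive statistics only.

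No new data, samples or subjects are needed, and standard software does the calculation. There are two small costs:

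- **Estimand.** Hodges-Lehmann estimates the pseudomedian. This equals the median difference only if the paired differences are symmetric, so the table label should name it correctly.
- **Documents.** Protocol 10.3.2.2 carries the same wording. Either align the protocol or record the departure in SAP section 11, where the statement that nothing changed would otherwise be untrue.
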